8.1. Documentation

Source data will include both hard copy and electronic questionnaires and measures. The hard copy data will be retained in a locked filing cabinet at each study site. Electronic data will be directly input into the de-identified eCRF held on REDCap. De-identified data will be entered into a password protected electronic database. Research assistants will be responsible for entering data into the database and will be trained accordingly.

After data cleaning procedures are finished, the clinical trial database will be closed. All data will be exported into the appropriate software to enable statistical analysis.

8.2. Archiving

The coordinating investigator, project manager or their delegate shall arrange for the retention of documentation relating to the trial (source documents, informed consent forms, approvals) for 15 years. Archiving for all sites will take place within the IMPACT SRC at Barwon Health.

9. Statistical Methods and determination of sample size

9.1. Description of analysis sample

The sample to be included in the analyses will be all the participants who give consent to participate in the study who meet all inclusion criteria and no exclusion criteria, and who have taken at least one dose of trial medication and completed at least one post-baseline assessment.

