3.1.1. Aims

The primary aim of this study is to investigate the efficacy of adjunctive mangosteen pericarp 1000mg/day for the treatment of bipolar depression using a 24-Week randomised, placebo-controlled trial. The primary outcome measure will be the change in severity of mood symptoms, measured using the Montgomery Åsberg Depression Rating Scale (MADRS). Secondary outcomes include global psychopathology, substance use, functioning, quality of life, and safety and tolerability data. A follow-up interview will be conducted 4 weeks post-treatment to determine any outcomes following cessation of the trial agent.

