4.7. Assessment of safety

All adverse events will be recorded, intervened according to medical assessment, and monitored. Participants are asked open-ended questions about how they have been feeling in general and if they have any concerns regarding their health or the study medication. The DSMB will review the study reports and determine any safety issues if they arise.

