6.7. Frequency of visits and follow up period

Participants will be assessed at baseline, regular 4-weekly intervals throughout the 24-week trial (weeks 4, 8, 12, 16, 20, 24), and at a post-discontinuation follow-up 4 weeks after completion of the trial as outlined in Table 1. Interviews with participants will take an average of 40-60 minutes. If participants cannot be seen face-to-face due to safety concerns, interviews will be conducted via online platforms such as Zoom, Skype or over teleconference as a last resort. Once enrolled, participants will be reimbursed for travel up to the value of \$20, per visit, or to cover internet expenses. Visits must occur within one week of the pre-determined date (based on baseline visit date). If a visit occurs more than 7 days after the pre-determined date, this will be a deviation from protocol. If participants cannot attend any visit before 2 weeks from the pre-determined date, this visit will be skipped until the next scheduled assessment. A skipped visit will also be a deviation from protocol.

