6.8. Withdrawal of participants from treatment or assessment

Participants will be withdrawn from the trial if they; discontinue the trial medication for >7 days; cease effective contraception, become pregnant or withdraw consent.

Discontinuation due to adverse events (both serious and non-serious) may be a criterion for withdrawal, but is not mandatory, and could be either at the request of the participant or the discretion of the investigator. Withdrawal of consent will not require any data to be destroyed. This instead is termed 'revocation of consent' and has an associated form to be completed.

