6.13.2.1. Recording of adverse events

Adverse events will be collected from the time that Informed Consent has been obtained until the end of the 24 week intervention period. At each visit, participants will be asked if they have had any health problems since the previous visit. All AEs will be recorded appropriately, whether or not considered related to the investigational product. This will include AEs spontaneously reported by the participant and/or observed by the staff as well as AEs reported in response to a direct question e.g. "Have you had any health problems since your last visit". The current study also encourages reports of unexpected improvements as part of the AE reporting.

For each AE the following parameters will be described: a description of the event, start and stop date, action taken with regards to investigational product (if applicable), outcome, if the AE caused the patient to discontinue, a statement if the AE fulfils the criteria for a SAE or not, the treating doctor or investigator's assessment of the causal relationship between the event and the investigational product, treatment for the AE and the intensity of the AE.

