9.2. Method of statistical analysis

All analyses will be conducted in accordance with the International Conference on Harmonization E9 statistical principles, and are based on all randomised participants with at least one post-baseline observation (intention to treat population). Reporting of research findings will be done in accordance to CONSORT guidelines. The statistician responsible for the analysis of outcome data will be blind to group allocation. The primary efficacy analysis will assess average treatment group differences for the primary outcome measure MADRS total score over the entire study period and will use a likelihood based mixed-effects model, repeated measures approach (MMRM). The MMRM model includes the fixed, categorical effects of treatment, investigator, visit, and treatment-by-visit interaction, as well as the continuous, fixed covariates of baseline score and baseline score-by-visit interaction. The MMRM includes all available data at each time point and is the preferred method of analyzing clinical trial data in psychiatry as compared to more traditional repeated measures analysis of variance (ANOVA) and analysis of covariance models (ANCOVA). Planned comparisons will be done with the MMRM models to determine between group differences in change of symptoms measures from baseline to week 24. Results from the analysis of dichotomous data will be presented as proportions, with 95% confidence interval, and Fisher's exact p-value where appropriate. Non-parametric statistics will be used when assumptions for parametric methods are violated. Effect sizes will be calculated using Cohen's guidelines. All tests of treatment effects will be conducted using a two-sided alpha level of 0.05 and 95% confidence intervals. Change scores in symptoms and in biological markers will be derived. Pearson Product Moment Correlations will be used to examine the relationships between the change scores for symptoms and the change scores for biological markers in the two groups. Using Fisher's z transformation, we will test whether the correlations obtained for each group are statistically different in terms of strength.

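### As worded, the post-baseline condition in sections 9.1 and 9.2 also covers safety, so dosed participants who leave before about week 4 would be missing from the comparative safety results

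*Protocol*

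**What the plan says.** Section 9.1 of the protocol describes a single sample for the analyses. Beyond consent and eligibility, it admits only those "who have taken at least one dose of trial medication and completed at least one post-baseline assessment". Section 9.2 opens with a rule for every analysis: they "are based on all randomised participants with at least one post-baseline observation (intention to treat population"). Neither section defines a separate safety set or mentions adverse events.

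Section 3.1.1 places safety among the outcomes: "Secondary outcomes include global psychopathology, substance use, functioning, quality of life, and safety and tolerability data".

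On timing, section 6.7 sets assessments at baseline and at "regular 4-weekly intervals throughout the 24-week trial (weeks 4, 8, 12, 16, 20, 24"), and adds "Visits must occur within one week of the pre-determined date". Section 6.8 withdraws participants who "discontinue the trial medication for >7 days" and allows for withdrawal because of adverse events.

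On data collection, section 6.13.2.1 says "Adverse events will be collected from the time that Informed Consent has been obtained until the end of the 24 week intervention period". On oversight, section 4.7 says "The DSMB will review the study reports and determine any safety issues if they arise".

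**The concern.** A post-baseline condition is common for a repeated-measures efficacy model, because a participant with no post-baseline score contributes little to it. It suits safety poorly. Whether a participant reaches the first visit is decided after dosing, and intolerance is one plausible reason for not reaching it. The condition can therefore remove the participants whose experience matters most to a tolerability comparison, from numerator and denominator alike.

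At stake are the analysed and published safety and tolerability results. The primary MADRS result and the power calculation are not affected.

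**Working it through.** The point rests on definitions, so the sections are compared first. The arithmetic then shows what scale is possible.

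**1. Does the rule reach safety?** Section 9.2 covers all analyses without exception. Section 9.1 offers only one sample. Section 3.1.1 makes safety and tolerability a secondary outcome. Taken together, a safety comparison falls under the rule. This is an inference from the scope of the wording, since section 9 never names safety.

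**2. Can a dosed participant leave before any post-baseline assessment?** Section 6.10 supplies medication after the baseline visit and randomisation. The first scheduled assessment is week 4, and with the one-week window that means about weeks 3 to 5. Section 6.8 withdraws a participant after more than seven days off medication. Section 4.6 puts the threshold at seven consecutive days. Those two passages should be reconciled, but under either one a participant can be dosed, stop and be withdrawn before week 3.

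**3. Are the events in the database?** Yes. Collection starts at consent (6.13.2.1), and section 6.13.2.2 provides follow-up to resolution or to 7 days after completion or withdrawal. The analysis rule, not the data collection, leaves these participants out.

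**4. How many might be affected?** The only attrition figure is 20% for the whole study (9.3). It reproduces the recruitment target: 120 / (1 − 0.20) = 150. Expected losses are 150 × 0.20 = 30. The protocol does not say when they occur, so the early share is assumed, as is that all early leavers had taken at least one dose:

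| Assumed share of attrition before the first visit | Missing from safety results | Share of 150 |
|---|---|---|
| 1/6 | 30 × 1/6 = 5 | 3.3% |
| 1/3 | 30 × 1/3 = 10 | 6.7% |
| 1/2 | 30 × 1/2 = 15 | 10.0% |

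**5. What happens to the rates?** Suppose x of n participants in an arm have the event, and k of those x leave early. The rate changes from x/n to (x − k)/(n − k), which is lower whenever k > 0 and x < n. So each arm's rate falls if its early leavers are the ones with events. The between-arm difference depends on k in each arm. Two cases with assumed counts and 75 per arm (1:1 allocation of 150):

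| Case | All dosed | Under the rule | Difference, all dosed | Difference, under the rule |
|---|---|---|---|---|
| A: 8 active and 2 placebo events; half of each leave early (4 and 1) | 8/75 = 10.7%; 2/75 = 2.7% | 4/71 = 5.6%; 1/74 = 1.4% | 8.0 points | 4.3 points |
| B: 11 active and 7 placebo events; 3 in each arm leave early | 11/75 = 14.7%; 7/75 = 9.3% | 8/72 = 11.1%; 4/72 = 5.6% | 5.3 points | 5.6 points |

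If one-sixth or one-third of the case A events led to early departure, the same formula with fractional expected counts gives 6.67/73.67 − 1.67/74.67 = 6.8 points and 5.33/72.33 − 1.33/74.33 = 5.6 points. In case A, where early loss differs by arm, the difference shrinks. In case B, where it is equal, the difference does not shrink, although both rates are understated.

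**The case against.** The strongest reply is that section 9 is about efficacy. After its opening sentences, section 9.2 covers the MADRS model, symptom comparisons, dichotomous data, effect sizes and biomarker correlations. Section 4.4 leaves safety out of its secondary outcomes, none of the secondary hypotheses in 3.1.3 concerns it, and it has its own sections. Safety sets are commonly left to the SAP, which is not at hand. This stands in part: the protocol does not expressly decide to drop safety data, and the reading comes from the breadth of its wording. But the rule is stated for all analyses, so a SAP that used all dosed participants for safety would depart from the protocol as written.

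A second reply is that section 9.2 asks for a post-baseline *observation* and section 9.1 for a completed *assessment*. An adverse event reported between visits might count as the former, though not clearly as the latter. This also stands. The two sections do not define the same set: 9.1 requires eligibility and dosing, while 9.2 speaks of all randomised participants. That is a further reason to clarify.

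A reader might infer that early leavers vanish from the safety record altogether. The protocol does not support that. Their events are recorded, serious events go to regulators and ethics committees (6.13.3), and the DSMB reviews study reports and adverse effects (4.7, 6.10.3). The loss is confined to the comparative results.

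A reader might also infer that the rule necessarily pushes the comparison toward no difference. Case B shows that it need not.

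**Conclusion.** The point holds as a defect of wording with a real consequence. Followed literally, sections 9.1 and 9.2 leave dosed participants without a post-baseline assessment out of the safety comparison. Confidence is moderate, because the application to safety is inferred from scope and not stated.

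The size cannot be computed from the protocol. The range of 5 to 15 participants out of 150 rests on the assumed early share of the 20% attrition, and the event counts in cases A and B are illustrations only. Understatement of an arm's rate requires that its early leavers are disproportionately those with events. If they had none, removing them would raise the rate. Distortion of the difference depends on how early loss compares between arms, and the protocol gives no figure for that.

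**What to change.** In sections 9.1 and 9.2, limit the post-baseline condition to efficacy analyses. Add one sentence saying that safety analyses include every participant who took any trial medication, whether or not a post-baseline assessment followed. In the same edit, make the two sections describe the same efficacy set and use one term for what counts as post-baseline data. Make the change before the blind is broken, and carry it into the SAP.

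The cost is a short text amendment. The adverse event data are already collected from consent onward, and sample size, power, visits and procedures do not change.

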9.2. Method of statistical analysis

All analyses will be conducted in accordance with the International Conference on Harmonization E9 statistical principles, and are based on all randomised participants with at least one post-baseline observation (intention to treat population). Reporting of research findings will be done in accordance to CONSORT guidelines. The statistician responsible for the analysis of outcome data will be blind to group allocation. The primary efficacy analysis will assess average treatment group differences for the primary outcome measure MADRS total score over the entire study period and will use a likelihood based mixed-effects model, repeated measures approach (MMRM). The MMRM model includes the fixed, categorical effects of treatment, investigator, visit, and treatment-by-visit interaction, as well as the continuous, fixed covariates of baseline score and baseline score-by-visit interaction. The MMRM includes all available data at each time point and is the preferred method of analyzing clinical trial data in psychiatry as compared to more traditional repeated measures analysis of variance (ANOVA) and analysis of covariance models (ANCOVA). Planned comparisons will be done with the MMRM models to determine between group differences in change of symptoms measures from baseline to week 24. Results from the analysis of dichotomous data will be presented as proportions, with 95% confidence interval, and Fisher's exact p-value where appropriate. Non-parametric statistics will be used when assumptions for parametric methods are violated. Effect sizes will be calculated using Cohen's guidelines. All tests of treatment effects will be conducted using a two-sided alpha level of 0.05 and 95% confidence intervals. Change scores in symptoms and in biological markers will be derived. Pearson Product Moment Correlations will be used to examine the relationships between the change scores for symptoms and the change scores for biological markers in the two groups. Using Fisher's z transformation, we will test whether the correlations obtained for each group are statistically different in terms of strength.

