3.1.2. Primary Hypothesis

i) 24-Weeks of adjunctive mangosteen pericarp treatment will be superior to placebo in depression, as measured using the MADRS.

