4.4. Efficacy Variables

The primary outcome variable will be the MADRS total score at the end of the 24-week treatment phase.

Secondary outcomes include the Bipolar Depression Rating Scale (BDRS), Young Mania Rating Scale (YMRS) and Hamilton Anxiety Rating Scale (HAM-A) scores. Participant life satisfaction will be rated on the self-reporting scale (Q-LES-Q). Functioning measures will include the Social and Occupational Functioning Assessment Scale (SOFAS), and Longitudinal Interval Follow-Up Evaluation-Range of Impaired Functioning Tool (LIFE-RIFT). The Clinical Global Impressions Bipolar Version (CGI-BP) will be used to rate clinician judgement for improvement and severity of illness. The Patient Global Impression Scale (PGI) will be used to rate participant perception. We will ask participants to complete a number of pen and paper based cognitive tasks; digit span forwards and backwards, trail making and the Symbol Digit task.

In order to undertake a cost-utility analysis (CUA), gains in utility for the participants will be measured in the study. The most common metric developed to measure utility gains from health interventions is the QALY. A QALY is simply calculated by multiplying the period of time spent in a particular health state by the "utility" or preference value assigned to that health state measured on a scale from 0 (denoting death) to 1 (denoting full health). There are different techniques of deriving utility however the simplest is via the use of a multi-attribute utility instrument which is basically a health related quality of life measure (HRQoL) which has pre-determined "weights" assigned to the health states included within the measure – this is called indirect elicitation of utility. We propose to use the AQol4D to assess any utility based HRQoL gains. It comprises four separately scored dimensions, consisting of independent living, relationships, mental health, and senses. It consists of 12 items and takes 2 minutes to complete. The main utility algorithm of the AQoL has been scored using the time trade off method and the questionnaire has sound psychometric properties. The AQoL4D will be administered to study participants at baseline, 12 and 24 weeks. Scoring will be completed with the algorithm provided by the developers of the instrument obtained from: http://www.aqol.com.au/scoring-algorithms.html .

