4.8. Assessment of predictors and moderators

- The Standardised Assessment of Personality Abbreviated Scale (SAPAS) will be used to identify those with suspected personality disorders and this will be used as a covariate in the analysis and also used as a variable of interest in examining treatment response.
- The Dietary Questionnaire for Epidemiological Studies Version 2 (DQES v2) is a self-administered paper based modification of the food frequencies questionnaire developed by the Cancer Council to measure dietary intake. Diet quality can then be used as a covariate in the analysis and also used as a variable of interest in examining treatment response.
- Analysis of biomarkers of oxidative and inflammatory markers will be used to determine how treatment response (if present) correlates to changes in biological markers.
- Changes in biomarkers will be used to explore the underlying pathophysiology of depression.

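### The primary outcome is MADRS at week 24, but the primary analysis tests the average MADRS difference over the whole study period

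*Protocol*

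**What the plan says.** Section 4.4 fixes the outcome at one time point: "The primary outcome variable will be the MADRS total score at the end of the 24-week treatment phase". Table 1 (section 4.9) agrees: it heads the week-24 visit as the primary end-point and weeks 4 to 20 as interim assessments.

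Section 9.2 defines the primary efficacy analysis differently: "The primary efficacy analysis will assess average treatment group differences for the primary outcome measure MADRS total score over the entire study period". It then adds: "Planned comparisons will be done with the MMRM models to determine between group differences in change of symptoms measures from baseline to week 24". That sentence covers symptom measures in general and does not say whether the week-24 MADRS contrast is primary or secondary.

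The model can deliver either quantity: "The MMRM model includes the fixed, categorical effects of treatment, investigator, visit, and treatment-by-visit interaction", together with baseline score and its interaction with visit. On error control, 9.2 says: "All tests of treatment effects will be conducted using a two-sided alpha level of 0.05 and 95% confidence intervals". No order of testing is given.

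Separately, section 4.8 says of the SAPAS personality screen that "this will be used as a covariate in the analysis and also used as a variable of interest in examining treatment response". The model terms listed in 9.2 do not include it.

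**The concern.** The definition of the outcome and the definition of the primary test should lead to the same number. Here they do not. Because the model has a treatment-by-visit term, the week-24 difference and the difference averaged over visits are two separate contrasts with separate estimates and p-values. Someone following 9.2 as written would test a quantity other than the outcome declared in 4.4, and someone following 4.4 would promote a contrast that 9.2 does not call primary. A later analysis plan could follow either section and would contradict the other.

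At stake is which result decides the trial. If the effect develops slowly, the average is diluted by the early visits. If it appears early and holds, the average is the more precise measure. The two tests can then fall on opposite sides of 0.05.

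**Working it through.** **Does another section settle it?**
- The aims (3.1.1) define the primary measure as change in severity on the MADRS, with no time point.
- The primary hypothesis (3.1.2) reads "24-Weeks of adjunctive mangosteen pericarp treatment will be superior to placebo in depression, as measured using the MADRS". This gives a duration of treatment and fits either contrast.
- The power statement (9.3) refers to a difference in MADRS score without naming a visit.

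So 4.4 and Table 1 stand on one side, 9.2 on the other, and nothing decides between them.

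**Inputs from the protocol.** Six post-baseline treatment visits (weeks 4, 8, 12, 16, 20, 24; section 6.7); d = 0.362, two-sided 0.05, 80% power, 120 evaluable participants (9.3); 1:1 allocation (6.6), hence 60 per arm.

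**Assumptions (the protocol gives none of these).** Between-visit correlation r of 0.3 to 0.9, compound symmetry (CS) or AR(1); unit variance; complete data; week-24 effect of 0.362; effect either constant over visits or growing linearly from zero at baseline.

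**The protocol's own figure.** n per arm = 2 × ((1.96 + 0.8416)/0.362)² = 119.8, so 120 per arm. With 60 per arm, power = Φ(0.362 × √(60/2) − 1.96) = Φ(0.023) = 51%. The stated 80% with 120 in total is therefore not reproduced. That is a separate problem, and the mismatch described here does not depend on it; 60 per arm is used below only because it is the protocol's evaluable number.

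**Size of the average under linear build-up.** Mean of (1, 2, 3, 4, 5, 6)/6 = 0.583. The average effect is 0.583 × 0.362 = 0.211, or 58% of the week-24 difference.

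**Power at CS with r = 0.5, no baseline adjustment.** The variance of the six-visit mean is (1 + 5 × 0.5)/6 = 0.583, and power = Φ(effect × √30/√variance − 1.96).

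**The same with baseline adjustment**, if r = 0.5 also holds between baseline and each later visit. The baseline removes 0.5² = 0.25 from each variance and covariance, leaving 0.75 at week 24 and 0.583 − 0.25 = 0.333 for the mean.
- Week 24: 0.362 × √30/√0.75 = 2.29; power Φ(0.33) = 63%.
- Average, linear: 0.211 × √30/√0.333 = 2.00; power Φ(0.04) = 52%.
- Average, constant: 0.362 × √30/√0.333 = 3.43; power Φ(1.47) = 93%.

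| Test | No baseline adjustment | With baseline adjustment |
|---|---|---|
| Week 24 | 51% | 63% |
| Average, linear build-up | 33% | 52% |
| Average, constant effect | 74% | 93% |

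Over both correlation structures and r = 0.3 to 0.9, without baseline adjustment, the average has 23–60% power under linear build-up and 54–97% under a constant effect.

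**How far the two tests agree when there is no effect.** Under CS the correlation of the two test statistics is √((1 + 5r)/6), which is 0.764 at r = 0.5. It runs from 0.65 to 0.96 under CS and from 0.45 to 0.86 under AR(1).

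**If either test at 0.05 were allowed to decide.** Type I error = 1 − P(|Z₁| < 1.96 and |Z₂| < 1.96). This is 8.0% at CS 0.5, and 6.4% to 9.2% over the whole range.

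**The case against.** Several stronger readings are tempting, and the text does not carry them.

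- **Two primary tests.** A reader might infer that the trial has two tests both called primary, so that the 0.05 level already fails. Section 9.2 labels only the average as the primary efficacy analysis, and nothing permits choosing whichever result is significant. The 6–9% describes a possible misuse, not the plan. What stands is that all tests carry 0.05 with no ordering, and the declared outcome points to the contrast that 9.2 does not label.
- **The hypothesis fixes week 24.** It does not, since it states a treatment duration. The evidence for week 24 is section 4.4 and Table 1.
- **Week 28 enters the average.** MADRS is measured at the post-discontinuation visit, and 9.2 uses all available data. But sections 5.3 and 6.7 schedule that visit after the study or trial is complete, so weeks 4 to 24 is the natural reading of the study period. A clarifying clause is enough.
- **The average always loses power.** It does not: under a constant effect it has more. The unadjusted figures also understate power under the planned model, which includes baseline.
- **SAPAS belongs to the same fault.** It is a separate and weaker point. Section 4.8 speaks of the analysis without naming the primary model, and says only that diet quality can serve as a covariate.

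One could add that using an MMRM is sound. It is; the treatment-by-visit term is what makes the week-24 contrast available.

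**Conclusion.** The protocol is wrong as written on this point: its primary outcome (4.4, Table 1) and its primary analysis (9.2) are different quantities, and no other section reconciles them. That finding needs no assumption.

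The size of the consequence does. Under linear build-up the average captures 58% of the week-24 difference; at CS 0.5 and 60 per arm this costs 18 percentage points of power without baseline adjustment (51% to 33%) and 11 with it (63% to 52%). Under a constant effect the average gains 23 and 30 points instead. The direction therefore rests on an effect shape and correlations that the protocol does not give. In every case examined the two tests are imperfectly correlated, so they can lead to different conclusions. The documents do not support saying that type I error is already inflated; they support saying that the deciding test is not consistently defined.

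**What to change.** In section 9.2, state that the primary analysis is the week-24 treatment contrast in MADRS total score, estimated from the MMRM with the listed terms fitted to weeks 4 to 24. This matches 4.4 and Table 1. Name the visit-averaged effect as a secondary analysis, and state that the week-28 assessment is analysed separately. In 9.3, say that the power statement refers to the week-24 contrast.

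As a separate minor correction, reconcile 4.8 with 9.2 by stating whether SAPAS is in the primary model.

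The cost is about one paragraph of protocol wording. The model, the data and the visits stay the same. The change should be made before unblinding.
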